### Secondary Study Endpoints:

- Exercise session adherence rate among the Exercise Group, collected from the Maple Tree Cancer Alliance participant records.
- Exercise program attrition rate among the Exercise Group, collected from the Maple Tree Cancer Alliance participant records.

### Safety endpoints are:

- Objective worsening lymphedema due to physical activity, as determined by treating oncologist
- Pathologic fracture
- Recommendation to stop physical activity by treating oncologist

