### Demographic and Baseline Clinical Characteristics:

- Age, as determined via electronic medical record (EMR)
- Diagnosis and diagnostic stage, as determined via EMR
- Diagnosis Date, as determined via EMR
- Body mass index, as determined by height and weight in EMR
- Comorbid chronic conditions (hypertension, diabetes, COPD), as determined via EMR
- Race/ethnicity, as determined via EMR

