### Control Group

The control group will receive the current standard of care, which includes a resource guide with various options available to the cancer survivor. Within this guide are tips for healthy eating and pictures of standard exercises to improve fitness.

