## 6.0 Procedures Involved\*

The study design is an open-label, randomized, controlled, parallel-group trial. Women age 30-80 with a recent diagnosis of stage 0, 1 or 2 breast cancer who meet inclusion and exclusion criteria will be invited to participate. As is typical and customary, a diagnosis within the last 12 weeks will be considered a recent diagnosis. Upon study enrollment and informed consent, patients will be randomly assigned to the Exercise Group or the Control Group. Random assignment will be conducted in blocks of 10 to ensure equal groups (See Appendix A). Participants will be enrolled in the study for 12 weeks.

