## 15.0 Risks to Subjects\*

The risks associated with the study intervention are commensurate with light to moderate physical activity, such as muscle soreness. Given the low-impact nature of the exercise and the one-on-one supervision during exercise sessions, the risk of injury or another adverse outcome is very low. Participants in the Exercise Group will have an exercise program individualized to their needs and physical abilities, and participants will be closely monitored during exercise sessions. The

**PROTOCOL TITLE:** Randomized, Controlled Trial of an Individualized Exercise Oncology Program for Newly Diagnosed Breast Cancer Patients

study will not be blinded; patients and treating physicians will be aware of group status and if the treating oncologist recommends the subject stop physical activity, the subject will be withdrawn from the study.

The Exercise Group may incur some travel costs to attend exercise sessions.

No psychological, social, or legal risks are anticipated.

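### The lymphedema safety endpoint counts only worsening that an unblinded oncologist attributes to physical activity, so it cannot give an unbiased comparison of lymphedema between arms

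*Combined protocol and SAP*

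**What the plan says.** Section 4.0 lists three safety endpoints:

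- "Objective worsening lymphedema due to physical activity, as determined by treating oncologist"
- "Pathologic fracture"
- "Recommendation to stop physical activity by treating oncologist"

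Section 6.0 describes the design: "The study design is an open-label, randomized, controlled, parallel-group trial". Section 15.0 adds that "patients and treating physicians will be aware of group status".

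Under Section 5.0 the Exercise Group has weekly one-on-one supervised sessions that include full-body strength training. Controls receive a resource guide: "Within this guide are tips for healthy eating and pictures of standard exercises to improve fitness".

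Section 14.0 applies the safety endpoints to every study patient, in either arm, and makes each one a reason for withdrawal. Final measures other than physical activity are still collected after withdrawal.

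The baseline list in Section 4.0 includes "Comorbid chronic conditions (hypertension, diabetes, COPD), as determined via EMR" but not lymphedema status. The data analysis plan in Section 17.0 gives general between-group tests and no dedicated safety comparison. Section 18.0, on safety monitoring, is marked not applicable.

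**The concern.** Randomisation makes the two arms comparable for lymphedema as long as cases are counted by the same rule in both. Here a case counts only after the treating oncologist has decided that activity caused it. That physician knows who is in the exercise program, and a control patient has no study exercise to blame. The same arm swelling is therefore more likely to count in one arm than in the other.

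The error can go either way. If oncologists readily blame the sessions, the endpoint shows an excess where none exists. If they put swelling down to cancer treatment, a real excess in the Exercise Group disappears from the count. In both cases the result reflects how causes were assigned as well as how many patients worsened.

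The recommendation to stop activity is uneven in a related way, because it arises more naturally for a patient in a supervised program. Both endpoints lead to withdrawal, so uneven counting can also make withdrawal differ by arm.

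**Working it through.** **No figure in the plan to reproduce.** The documents give no lymphedema rate, no probability of attribution and no sample-size reasoning for safety. The stated 80% power concerns missed treatment fractions and has no bearing here.

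**Step 1. Does the counting rule treat the arms alike?**

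| Feature | Exercise Group | Control Group | Source |
|---|---|---|---|
| Supervised study exercise | Weekly, one-on-one | None; guide with exercise pictures | Section 5.0 |
| Attribution to activity required | Yes | Yes | Section 4.0 |
| Physician knows the arm | Yes | Yes | Section 15.0 |
| Endpoint applies | Yes | Yes | Section 14.0 |

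The rule has the same wording for both arms, but the candidate cause differs between them, and the oncologist who assigns the cause knows which arm the patient is in.

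**Step 2. How large could the distortion be?** Inputs: 35 patients per arm (Section 12.0). The true worsening rate *p*, equal in both arms, and the proportion *a* of cases attributed to activity are assumptions. Attribution in controls is set to 0.

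Expected count in the Exercise Group = 35 × *p* × *a*. Expected count in controls = 35 × *p* × 0 = 0.

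| *p* | True cases per arm | Counted, *a* = 0.5 | Counted, *a* = 1 |
|---|---|---|---|
| 5% | 35 × 0.05 = 1.75 | 0.875 vs 0 | 1.75 vs 0 |
| 10% | 35 × 0.10 = 3.5 | 1.75 vs 0 | 3.5 vs 0 |
| 20% | 35 × 0.20 = 7 | 3.5 vs 0 | 7 vs 0 |

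**Step 3. Could this produce a nominally significant false signal?** By Fisher's exact test with 35 per arm, 5 vs 0 gives p = 0.054 and 6 vs 0 gives p = 0.025. The chance of 6 or more counted exercise cases, with no true difference, is P(X ≥ 6) for X ~ Binomial(35, *p* × *a*):

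- *p* = 10%: 0.7% if *a* = 0.5, and 13% if *a* = 1.
- *p* = 20%: 13% if *a* = 0.5, and 73% if *a* = 1.

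**Step 4. The opposite error.** Suppose that exercise doubled the rate from 10% to 20%, and that every case was attributed to cancer treatment. The truth is 35 × 0.20 = 7 against 35 × 0.10 = 3.5. The endpoint shows 0 against 0.

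**Step 5. What would an all-cause count achieve?** With equal true rates and equal detection, the expected counts are equal. Precision remains poor. For 20% against 10%, the standard error of the difference is √(0.20 × 0.80/35 + 0.10 × 0.90/35) = 0.0845. The 95% confidence interval is 0.10 ± 1.96 × 0.0845, or about −6.6 to 26.6 percentage points. Power of Fisher's exact test for that difference is about 13%.

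**The case against.** **These endpoints work as withdrawal triggers.** Section 14.0 is the only place where the protocol puts them to use. H1 contains no safety hypothesis, and Section 17.0 names no safety comparison. For a decision about one patient's activity, asking whether activity caused the worsening is defensible. This stands, and it is why the remedy should be a separate outcome. Redefining the endpoint itself would widen the withdrawal trigger to worsening of any cause in both arms. It does not rescue the endpoint as a comparative measure, and the plan has no other measure that names lymphedema.

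**Harm can be compared on other measures.** A reader might infer that the arms cannot be compared for harm at all. The documents do not support that. Pathologic fracture has no attribution clause, and ER visits, hospital encounters and treatment-related side effects come from the EMR with no exercise attribution. The side-effects endpoint might capture some lymphedema, but it does not name it and carries its own attribution, to cancer treatment.

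**Controls are not excluded.** A reader might also infer that worsening in controls can never count. Section 14.0 covers both arms, and a control could exercise from the guide and have swelling attributed to it. Unequal counting is a tendency.

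**The stop-activity endpoint may already reflect safety.** A reader might infer that it mixes harms with pauses unrelated to safety. The text speaks of stopping and mentions no such pauses. What remains is that the plan does not ask for the reason.

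**The oncologist may know the starting point.** The absence of lymphedema from the baseline list does not show that the treating oncologist lacks one. It shows only that the study dataset is not planned to hold it.

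**The numbers are assumed, and a fix will not give a powerful test.** Both are true. At 10% with half attributed, a false signal of 6 or more against 0 has a chance of only 0.7%, and 2 vs 0 gives p = 0.49. Even after the fix, 7 vs 3 gives p = 0.31 and 7 vs 4 gives p = 0.51. The gain is a count whose meaning is the same in both arms.

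**Conclusion.** The point holds for the lymphedema endpoint. As defined, it does not allow an unbiased between-arm comparison, because counting depends on a causal judgement by a physician who knows the arm, and supervised exercise exists in one arm only. This conclusion rests on the text and needs no assumed rate.

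The size is uncertain. At assumed true rates of 5% to 20% in both arms, with half of the exercise cases and no control cases attributed, the spurious difference is about 1 to 3.5 expected cases. It reaches 7 if every exercise case is attributed at the 20% rate. The direction cannot be predicted, since under-attribution would hide a real excess.

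The change is worth making because it is cheap and the trial otherwise has no even-handed lymphedema count. It does not bear on pathologic fracture or on the EMR utilisation endpoints.

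**What to change.** - Add a separately reported safety outcome: objective worsening of lymphedema documented in the EMR from randomisation to week 12, in both arms, regardless of presumed cause. State what counts as objective worsening. Include patients withdrawn under Section 14.0.
- Keep the oncologist's attribution as a separate descriptive field.
- Abstract lymphedema status at enrolment from the EMR and add it to the baseline list.
- Record the reason for each recommendation to stop activity.
- Report counts by arm with a 95% confidence interval for the difference, and label the comparison descriptive.
- Leave the Section 14.0 withdrawal trigger unaltered by this change. The sponsor should reconcile Sections 4.0 and 14.0 so that the comparative outcome and the withdrawal trigger are distinct.

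**Cost.** Protocol wording and a few more fields in the EMR abstraction, with no new visit or procedure. The raw count will rise in both arms, because it will include cases unrelated to exercise. Some open-label detection bias will remain: physicians know the arm, and Exercise Group patients are seen weekly by a trainer, so worsening may be noticed and documented more often in that group.

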## 5.0 Study Intervention/Investigational Agent

### Exercise Group

The study intervention is a supervised, individualized exercise oncology program described in previous literature and provided by Maple Tree Cancer Alliance, a non-profit organization providing exercise training to individuals with cancer (<https://www.mapletreecanceralliance.org/>). This organization was founded in 2011 and currently operates in 9 hospitals serving Ohio and Pennsylvania, offering free exercise programs and nutritional guidance to approximately 500 patients annually to help relieve side effects related to cancer treatment.

Patients in the supervised, individualized exercise oncology program (Exercise Group) will complete a 60-minute exercise session once per week for 12 weeks at Maple Tree Cancer Alliance. The exercise sessions will be individualized to the patient's needs and fitness level by a trainer with a bachelor's degree in exercise science and a national certification for exercise oncology. A patient will work with the same trainer throughout the study, who will plan the patient's individualized exercise regimen, and who will provide one-on-one supervision for the duration of each 60-minute session. Each 60-minute session will include cardiovascular, strength, and flexibility training.

Cardiovascular exercise will be performed on a treadmill. The intensity level for the aerobic exercise ranges from 30-45% of the individual's predicted VO2max, controlled by heart monitors (model S810i; Polar Electro) and lasting 30 min. Strength training will involve a full body workout, with emphasis on all major muscle groups and employing machines, free weights, and resistance tubing. Patients will complete 3 sets of 10 repetitions for each strength exercise. Flexibility training will involve static stretching of all major muscle groups for 15-20 seconds at the completion of each workout.

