## 14.0 Withdrawal of Subjects\*

Any study patient who experiences a safety endpoint under section 4.0, including recommendation to stop physical activity by treating oncologist, will be withdrawn from the study. Final, non-physical activity measures will be collected on patients who are withdrawn.

As Maple Tree provides free services to patients undergoing cancer treatment, a patient withdrawn from the study for safety reasons could, at a later date and when it is deemed safe by her physician, again receive exercise services at Maple Tree (outside the study context).

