### Data Analysis Plan:

Data will be analyzed using IBM SPSS Statistics version 25.0. Continuous variables will be described using mean, median, standard deviation, and range. Nominal variables will be described using frequency and percentage.

Baseline demographic and clinical characteristics will be compared between treatment and control groups to establish equivalence; any statistically significant differences between study groups will be controlled statistically. Continuous endpoints will be tested for normality using Shapiro-Wilk tests. Differences between study groups on continuous endpoints will be evaluated using independent samples *t*-tests for normally distributed endpoints and Mann-Whitney *U* tests for non-normally distributed endpoints. Nominal endpoints will be compared between groups using chi-square tests. Alpha will be set to .05, two-tailed for all tests.

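### A recommendation to stop physical activity is a safety endpoint whatever its reason, so stops unrelated to exercise harm can be counted as safety events and are probably picked up more often in the Exercise Group

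*Combined protocol and SAP*

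**What the plan says.** Section 4.0 of the combined protocol and SAP lists three safety endpoints. The lymphedema item carries a cause: "Objective worsening lymphedema due to physical activity, as determined by treating oncologist". Pathologic fracture is a medical event. The third item is a management decision, "Recommendation to stop physical activity by treating oncologist", and has no condition on reason, cause or severity.

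Section 14.0 makes every safety endpoint a trigger for withdrawal, in either arm: "Any study patient who experiences a safety endpoint under section 4.0, including recommendation to stop physical activity by treating oncologist, will be withdrawn". Section 15.0 repeats the stop rule, again without a reason: "if the treating oncologist recommends the subject stop physical activity, the subject will be withdrawn from the study". Section 15.0 also says that "patients and treating physicians will be aware of group status".

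Under Section 5.0, Exercise Group patients "will complete a 60-minute exercise session once per week for 12 weeks at Maple Tree Cancer Alliance". The Control Group receives standard care with a printed resource guide that includes exercise pictures.

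The Data Analysis Plan in Section 17.0 has no safety paragraph. Its general rule is "Nominal endpoints will be compared between groups using chi-square tests", at a two-sided alpha of .05. Section 18.0 marks safety monitoring as not applicable.

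**The concern.** An oncologist may advise a patient to stop exercising because exercise harmed her, or for a reason unconnected with exercise, such as an intercurrent illness or recovery from surgery. Those examples are mine; the protocol gives none. As written, both kinds of stop meet the endpoint and look identical in the data, because nothing requires the reason to be recorded.

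Ascertainment is also likely to differ by arm. An oncologist who knows that a patient attends a weekly supervised session has something specific to stop. The same illness in a control patient will often prompt no such advice, and so no endpoint.

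At stake is the safety conclusion. A table or test of this item could show more safety events with exercise when no patient was harmed by it, and a real harm could be hidden among ordinary interruptions. With Section 18.0 not applicable, no planned review would sort the reasons, and a reason not written down at the time may not be recoverable.

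**Working it through.** **Text check.** The plan gives no expected rate, count or threshold for any safety endpoint, so there is no stated figure to reproduce. The places set side by side:

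| Place | Reason or cause required? |
|---|---|
| 4.0, lymphedema | Yes, physical activity |
| 4.0, pathologic fracture | Not stated, but it is a medical event |
| 4.0, stop recommendation | No |
| 14.0, withdrawal | No |
| 15.0, stop rule restated | No |

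No section asks for the reason to be recorded or adjudicated.

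**Inputs for the illustration.** From the documents: 35 patients per arm (Section 12.0) and two-sided alpha .05 (Section 17.0). Assumed, because the documents give nothing: the rates of stops unrelated to exercise harm, written q.

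**Step 1: how few events produce a significant result.** For a events in Exercise and 0 in Control, with 35 per arm, the uncorrected Pearson statistic is X² = 70·(35a)² / [35·35·a·(70 − a)] = 70a / (70 − a).

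- a = 4: 280/66 = 4.24, p = .039 (Fisher .114)
- a = 5: 350/65 = 5.38, p = .020 (Fisher .054; continuity-corrected .063)
- a = 6: 420/64 = 6.56, p = .010 (Fisher .025)

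Section 17.0 does not say whether a continuity correction applies. Uncorrected, 4 versus 0 is enough; by Fisher it takes 6 versus 0.

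**Step 2: chance of a significant excess in Exercise when every counted stop is unrelated to exercise harm.** Sum Bin(a; 35, q_E)·Bin(b; 35, q_C) over all pairs with a > b and p ≤ .05.

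| q Exercise | q Control | Uncorrected chi-square | Fisher |
|---|---|---|---|
| 10% | 0% | 47% | 13% |
| 15% | 0% | 79% | 43% |
| 20% | 0% | 94% | 73% |
| 10% | 2% | 28% | 7% |
| 15% | 2% | 56% | 27% |
| 20% | 2% | 77% | 53% |
| 10% | 5% | 12% | 3% |
| 15% | 5% | 31% | 14% |
| 20% | 5% | 52% | 33% |
| 5% | 2% | 5% | under 1% |

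The continuity-corrected chi-square gives the same percentages as Fisher in every row.

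**Step 3: how much of the count would not be harm.** Let h be an assumed true exercise-harm rate of 5% in both arms. The expected count per arm is 35·[1 − (1 − h)(1 − q)].

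- q = 0: 35 × 0.05 = 1.75
- q = 5%: 35 × (1 − 0.95 × 0.95) = 3.4, of which 1.66/3.41 = 49% is not exercise harm
- q = 10%: 35 × (1 − 0.95 × 0.90) = 5.1, of which 3.33/5.08 = 66% is not
- q = 20%: 35 × (1 − 0.95 × 0.80) = 8.4, of which 6.65/8.40 = 79% is not

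If q is the same in both arms there is no expected imbalance, but unrelated stops still sit in the count.

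**The case against.** The strongest reply is that the plan never sets up a harm count. H1 and H2 contain no safety hypothesis, Section 17.0 describes no safety table or test, and the only stated use of the item is to trigger withdrawal in Sections 14.0 and 15.0. This stands in part. A reader might infer that the plan commits to testing this item as a safety difference. The documents do not say so; a test follows only if the general wording on nominal endpoints is read to include the safety endpoints, which it neither does expressly nor rules out.

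A reader might also infer that these stops will fall mostly in the Exercise Group. The documents do not establish that. The rule covers patients in either arm, controls also receive exercise pictures, and no rate is given. Unequal ascertainment is a sound inference from the open-label design and a supervised program in one arm only, but its size is unknown.

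Third, Section 14.0 speaks of withdrawal for safety reasons, which suggests that a safety-motivated stop was meant. That is a fair reading of intent, but the definition does not carry it.

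Fourth, the highest probabilities need zero control events and an uncorrected chi-square. That is correct, and they should not be taken as the expected size.

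Finally, the three safety items are listed separately, and the EMR endpoints already capture side effects, ER visits and hospital encounters in both arms. It would therefore be too strong to say that exercise harm cannot be assessed at all. Any bias from this item also runs against the intervention, so it would not create a false claim of benefit.

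**Conclusion.** The point holds as a defect of definition and reporting. As written, a stop recommendation for any reason meets a safety endpoint. Because physicians know the group and only one arm has a supervised program, the item is likely to be ascertained unequally.

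The size cannot be derived from the documents. Under assumed unrelated-stop rates of 10–20% in Exercise and 0–5% in Control, a between-group test would show a significant excess with probability 12% to 94% (uncorrected chi-square) or 3% to 73% (Fisher). At 5% versus 2% the chance is 5% or less. These figures are conditional on such a test being run, which the plan allows but does not specify. If the item is only tabulated, the remaining problem is a count that mixes harm with ordinary interruptions and has no recorded reason by which to separate them. The change is worth making because it is cheap and alters what the trial can conclude about safety.

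**What to change.** Keep the item in Section 4.0, so that the withdrawal text in Sections 14.0 and 15.0 that relies on it is unaffected. Add the following to Sections 4.0 and 17.0:

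1. For each stop recommendation in either arm, record the medical event that prompted it and whether that was a new or worsening adverse event judged related to physical activity.
2. Report related stops as safety events. Report all other stops separately, by reason and by arm, with an unclear category.
3. Do not test the unqualified count between groups as a harm difference.
4. Base the between-arm safety comparison on medical events collected the same way in both arms: pathologic fracture, and the ER visits, hospital encounters and treatment-related side effects already taken from the EMR.

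Replacing the item with the event behind the recommendation would not work: that event is undefined for a control patient who received no recommendation, and deleting the item would leave Section 14.0 pointing at nothing.

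The cost is a few sentences and a little more abstraction. Section 17.0 obtains EMR data through a downloaded report, and Section 4.0 names no source for stop recommendations, so someone may have to read the note for each one. Some reasons will be unclear. Relatedness will be judged by a physician who knows the group, which is why the unrelated stops must be shown as well. No change to any clinical stop or withdrawal rule is proposed.
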